3.3 Confounders

“A confounder is a variable that (a) is causally related to the disease or condition under study independently of the exposure of interest or, as often occurs in practice, serves as a proxy measure for unknown or unmeasured causes, and (b) is associated with the exposure under study in the study population, but is not a consequence of this exposure. It

follows from (a) that within each level of the exposure under study, the confounder is related to the disease conditional on exposure level” (Kelsey et al., 1996). An example of confounding may better explain this phenomenon. Consider a study of cigarette smoking and lung cancer. Many factors that are related to cigarette smoking are independently related to lung cancer. For example, age is strongly associated with lung cancer, with the incidence rates of this cancer much higher among those 65 years of age and older. To assess the association between cigarette smoking and lung cancer, one must control for the effects of this potential confounder. If controlling for this factor does not affect the association between smoking and lung cancer, then there is little or no confounding effect present.

Two methods are used for controlling for confounding in cross-sectional studies: matching in the study design or adjustment in the analyses of the data. Matching is rarely used in cross-sectional studies for two reasons. First, these types of studies are often conducted in general population groups where information on potential confounding variables on individual participants is not known prior to sample selection. Second, information on the level of exposure is frequently unavailable at the outset of the study, so it is not feasible to divide subjects into groups based on levels of exposure for the purposes of matching. In this study, the only exposure information known in advance to sample selection is the current location of residence. This information will not be used for matching, but will be used in the sampling strategy where individuals will be grouped according to predefined boundaries of exposure.

The alternate approach for removing the effects of potentially confounding variables is to control for them in the analyses. This is typically the only feasible method available for controlling for confounding in a cross-sectional design. Two analytic methods are used to take into account the influence of confounding variables. Stratified analysis sometimes is employed to assess whether the effects are similar across each category of a variable of interest. Alternatively, multivariate modelling techniques can be used to examine correlations between variables and to evaluate changes in effects when other variables are taken into account. With a large series of variables, stepwise regression techniques are sometimes employed to objectively identify a series of adjustment variables. However, this will sometimes identify extraneous variables that have no biological rationale for being included in the model. An alternative approach uses a series of potential confounders identified apriori through a review of the scientific literature and examines the influence that each variable has on the measure of risk after it is entered into the model. Adjustment variables that change the risk estimates by at least 10% will be treated as confounders and included in the multivariate model. Possible collinearity of the adjustment factors will be examined by examining correlations between the confounders and by examining the changes in the standard errors of these variables in the multivariate model. Parameters estimated will be presented for unadjusted, minimally adjusted models (age and sex), and fully adjusted models (age, sex and other identified confounders).

A commonly used technique to adjust for differences in the age distribution of different populations for comparative purposes is called direct age standardization. We will make

use of all of the above techniques in this study to control for differences in the distributions of these confounding variables in the study populations. These methods are outlined in greater detail in several epidemiological textbooks (Kelsey et al., 1996; Lilienfeld and Stolley, 1994; Rothman and Greenland 2000).

3.3.1 Demographics

The previous example used for explaining the concept of confounding effects illustrates the need to control for demographics such as age and gender. These variables along with others, such as body mass index and socio-economic status will be controlled for in this study.

3.3.2 Lifestyle

Certain lifestyle choices may act as potential confounders in that they are related to the outcome of interest and the exposure being examined. Lifestyle information that will be collected in this study includes smoking status and alcohol use.

3.3.3 Current medical health status

Certain medical outcomes are related to one another, as is the case for the presence of heart disease and high blood pressure. If it is possible that high blood pressure could be related to an exposure of interest, it is best that high blood pressure be controlled for when examining heart disease with respect to that exposure.

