1.0 Rationale

Emissions from INCO have resulted in contamination of soils with nickel, copper, cobalt and arsenic covering a wide area in Port Colborne. Several studies have been conducted on the impact of INCO's emissions on soil, vegetation and human health risks associated with contamination. A relatively high proportion of Port Colborne residents have expressed concerns regarding their health and the health of their family members.

Both animal and human studies have characterized the relationship between the identified Chemicals of Concern (CoCs) and various health conditions. Nickel has been linked to respiratory ailments, including asthma, chronic bronchitis and emphysema in occupational settings (Cornell and Landis, 1984) and is a recognized cause of allergic contact dermatitis (ATSDR, 1997). The International Agency for Research on Cancer (IARC) recognizes some nickel compounds as human carcinogens. Cobalt has also been linked to allergic contact dermatitis (Schafer, Bohler, Ruhdorfer et al, 2001). Finally, arsenic, like nickel, is a recognized IARC human carcinogen, and also has been shown to underlie dermatological, neurological and cardiovascular health issues (for review, see (Goldfrank, 1998).

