3.2.2.5 Validation

The individual medical tests described above have been included both for their utility in measuring general health and health conditions associated with exposure to the CoCs, as well as for purposes of validation. That is, specific medical tests also can be used as objective measures to validate reported medical health information from the health

questionnaire that is subjective in nature (Moffat et al., 2000; Smith- Sivertsen et al., 2000).

Medical tests that will serve as validators in this study include:

- Bilirubin test: validates the jaundice question in the questionnaire,
- Plasma cotinine test: validates recent smoking history question in the questionnaire,
- Serum TSH and fT4 test: validates thyroid condition questions in untreated individuals,
- ECG test: validates history of heart attack question in the health questionnaire,
- CO breath test: validates recent smoking history question in the health questionnaire,
- FEV1/FVC/PEFR tests: help to validate chronic bronchitis, emphysema, chronic obstructive pulmonary disease, asthma and other respiratory questions from the health questionnaire, and
- Skin patch tests: validates contact dermatitis question from the health questionnaire.

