3.3.4 Medications

In this study, subjects will report their medication use in the health questionnaire. Medications could be related to both an exposure and a clinical health assessment. In these cases, the effect of the exposure may be masked by the use of a medication and thus make the relationship between the exposure and clinical outcome difficult to discern. One example in this study could be the presence of abnormal results when testing thyroid hormone levels. An individual may have results that are within normal ranges but that individual is taking thyroid medication. Thus, this potential confounder will need to be controlled for in the analyses.

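### Section 3.3.3 calls for adjusting heart disease for high blood pressure whenever it may be related to exposure, without excluding blood pressure that results from exposure, which the protocol's own confounder definition rules out

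*Protocol*

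**What the plan says.** Section 3.3 of the protocol defines a confounder in two limbs. It "is causally related to the disease or condition under study independently of the exposure of interest" (or stands in for such a cause), and it "is associated with the exposure under study in the study population, but is not a consequence of this exposure". The same section starts from candidate confounders chosen in advance from the literature. It keeps those that shift the risk estimate by at least 10%, and presents unadjusted, age- and sex-adjusted, and fully adjusted results.

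Section 3.3.3 then sets a rule for related medical conditions. The trigger is "If it is possible that high blood pressure could be related to an exposure of interest"; the consequence is that "it is best that high blood pressure be controlled for when examining heart disease with respect to that exposure".

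Section 3.3.4 turns to medication, with thyroid treatment as the example: "An individual may have results that are within normal ranges but that individual is taking thyroid medication". It concludes: "Thus, this potential confounder will need to be controlled for in the analyses". Section 3.2.2.5 handles treated people differently: "Serum TSH and fT4 test: validates thyroid condition questions in untreated individuals".

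Section 1.0 says that arsenic, a Chemical of Concern (CoC), "also has been shown to underlie dermatological, neurological and cardiovascular health issues". Section 1.2.1.3 says cobalt may be linked to altered thyroid function. Mock Table 5 (section 6.5.1) lists hypertension, heart disease and thyroid condition side by side as conditions compared between Area 3 and the rest of the city.

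**The concern.** The trigger in section 3.3.3 is any possible relation to exposure. That includes the case in which exposure raises blood pressure, so that blood pressure lies on the path from exposure to heart disease. The second limb of the section 3.3 definition excludes exactly that case. The protocol thus treats hypertension as a possible effect of exposure in Table 5 and as an adjustment variable in section 3.3.3.

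The 10% rule does not catch the problem. Removing a mediated path moves the estimate, so a strong enough mediator passes the rule and is kept as a confounder. The fully adjusted odds ratio would then describe only what remains after the blood pressure path is taken out, while being read as the association of CoC exposure with heart disease.

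Section 3.3.4 raises a related but different problem. It sees correctly that treatment hides abnormal hormone results. But thyroid medication ordinarily follows from the thyroid condition, and calling it a confounder to be controlled for invites entering it as a covariate, which does not undo the masking.

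**Working it through.** The protocol states no figure on this point, so there is nothing to reproduce. The check has three parts.

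**1. The texts compared**

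| Place | Rule | Consequence of exposure excluded? |
|---|---|---|
| 3.3, definition | associated with exposure, not a result of it | yes |
| 3.3, 10% rule | keep candidates that move the estimate by 10% or more | no |
| 3.3.3 | control for blood pressure if possibly related to exposure | no |
| Table 5 | hypertension compared by exposure area | treated as an outcome |

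**2. How far adjustment for a mediator moves the odds ratio (OR)**

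All inputs are assumptions: high blood pressure in 25% of the unexposed; heart disease in 4% of unexposed people without high blood pressure; blood pressure to heart disease OR 3; exposure to blood pressure OR 1.5 or 2.0; direct exposure OR 1.0 or 1.3.

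Formula: the risk in each exposure group is (1 − p) × risk without high blood pressure + p × risk with it, where p is the group's prevalence of high blood pressure. The total OR is the ratio of the resulting odds.

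Worked case (exposure to blood pressure OR 2.0, no direct effect):
- Prevalence in the exposed: odds (0.25/0.75) × 2 = 0.667, so p = 0.40.
- Risk with high blood pressure: odds (0.04/0.96) × 3 = 0.125, so risk 0.111.
- Unexposed risk: 0.75 × 0.04 + 0.25 × 0.111 = 0.0578, odds 0.0613.
- Exposed risk: 0.60 × 0.04 + 0.40 × 0.111 = 0.0684, odds 0.0735.
- Total OR: 0.0735/0.0613 = 1.20. Adjusted OR: 1.00. Fall: 1 − 1.00/1.20 = about 17%.

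The same formula for all four cases, where the adjusted OR equals the direct OR:

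| Exposure to blood pressure OR | Direct OR | Total OR | Adjusted OR | Fall |
|---|---|---|---|---|
| 1.5 | 1.0 | 1.11 | 1.00 | 10% |
| 1.5 | 1.3 | 1.43 | 1.30 | 9% |
| 2.0 | 1.0 | 1.20 | 1.00 | 17% |
| 2.0 | 1.3 | 1.55 | 1.30 | 16% |

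A simulation of 500,000 people per case agrees (falls of 9% to 10% and 16% to 17%). Adding an unmeasured common cause of blood pressure and heart disease raises the falls to about 13% to 22%. With no direct effect, the adjusted OR then passes the null, to 0.94 or 0.90.

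Weak paths give less. With the blood pressure to heart disease OR lowered to 2, no direct effect, and high blood pressure in 5% to 50% of the unexposed, the same formula gives falls of 2% to 7% (exposure to blood pressure OR 1.5) or 4% to 11% (OR 2.0). If exposure does not affect blood pressure, adjustment changes the OR by 0% to 2% in the simulation.

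**3. Thyroid medication**

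Simulated with assumed inputs: exposure shifts a latent hormone level by 0.2 or 0.5 standard deviations; 30% to 90% of abnormal people are treated and largely normalised. The outcome is an abnormal result.

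| Shift | Treated | True OR | Medication ignored | Medication as covariate | Treated counted as abnormal |
|---|---|---|---|---|---|
| 0.2 | 30% | 1.52 | 1.52 | 1.52 | 1.52 |
| 0.2 | 90% | 1.50 | 1.42 | 1.32 | 1.50 |
| 0.5 | 30% | 2.75 | 2.68 | 2.72 | 2.75 |
| 0.5 | 90% | 2.73 | 2.60 | 2.31 | 2.73 |

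Masking exists before any adjustment. The covariate does not reliably remove it and can deepen it. Counting treated people as abnormal recovers the true OR.

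**The case against.** Several counter-arguments have weight.

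- **The mediator is inferred.** Nowhere does the protocol say that a CoC raises blood pressure; it speaks of cardiovascular issues in general, and section 3.3.3 says related, not caused. Blood pressure that exposure does not cause can be a proper adjuster. This stands, and it narrows the defect to a rule that fails to exclude the causal case.
- **The total association stays visible.** Section 3.3 commits to unadjusted and age- and sex-adjusted estimates beside the fully adjusted ones. Table 5 adjusts for age and sex only, and the open list of adjusters in section 6.4 names neither blood pressure nor medication. This stands and lowers the severity. It does not repair the fully adjusted model.
- **The 10% rule applies only to confounders chosen in advance.** True, but section 3.3.3 itself puts blood pressure among the candidates.
- **Section 3.3.4 does not prescribe a covariate.** Control may mean stratifying, or restricting to untreated people as in section 3.2.2.5. Self-reported thyroid condition is also a separate questionnaire item, so treated people who report it are already cases there. Both points stand. A reader might infer that the protocol orders conditioning on the disease itself; the text does not go that far. It leaves the method open where one choice would not work.

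A reader might also infer that bias toward the null is certain, or that the 10% rule should be limited to variables that precede exposure. Neither follows. The estimate can cross the null when there are shared unmeasured causes. And in a cross-sectional survey of long-term residential exposure, smoking, alcohol use, body mass index and income cannot be shown to come first, so that limit could remove the ordinary confounders.

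**Conclusion.** The concern holds in a limited form. Section 3.3.3 admits a case that the section 3.3 definition excludes, and the 10% rule offers no protection when the mediated path is strong. If exposure raises blood pressure, the fully adjusted heart disease OR is not the total association and is usually too close to the null: by about 9% to 22% in the main scenarios, and by as little as 2% with weak paths. These sizes rest wholly on assumed inputs. For thyroid medication, the fault is an unspecified instruction under a confounder label, not a demonstrated bias.

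This should be fixed. It is not critical, because the primary objective is to describe health status, the exposure analyses are additional to it, and the less adjusted estimates are reported alongside.

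**What to change.** 1. In sections 3.3 and 3.3.3, state that conditions that may plausibly result from CoC exposure, such as high blood pressure, are left out of the main exposure-outcome models whatever the 10% rule shows.
2. Report a blood-pressure-adjusted heart disease model only as a secondary analysis, labelled as a direct-effect estimate.
3. Keep the usual confounders chosen in advance: age, sex, smoking, alcohol use, body mass index and socio-economic status.
4. In section 3.3.4, replace the general instruction to control for thyroid medication. Count users (questionnaire item 50u, Appendix 10.1) as having a thyroid abnormality in the abnormal-result analysis, and report TSH and fT4 levels in untreated people as a labelled sensitivity analysis.

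The cost is a few sentences of analysis text and one secondary model. Blood pressure, reported hypertension and medication use are already collected, so no new data are needed.

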3.3.4 Medications

In this study, subjects will report their medication use in the health questionnaire. Medications could be related to both an exposure and a clinical health assessment. In these cases, the effect of the exposure may be masked by the use of a medication and thus make the relationship between the exposure and clinical outcome difficult to discern. One example in this study could be the presence of abnormal results when testing thyroid hormone levels. An individual may have results that are within normal ranges but that individual is taking thyroid medication. Thus, this potential confounder will need to be controlled for in the analyses.

3.3.5 Additional Metals

Mercury, lead, and cadmium will be examined as a potential confounders in the search for association between the CoCs and any reported health effects.

Exposure to mercury in small amounts is common. Three distinct chemical forms exist: elemental, organic, and inorganic. The toxic manifestations depend on the form of mercury and the degree of exposure. Chronic exposure to mercury compounds can affect a variety of organ systems, most notably the nervous system, kidneys, skin, and gastrointestinal systems (Clarkson, 1977; Baselt, 2000; Sue, 2002). Mercury is also a recognized teratogen.

Lead-induced disease typically occurs after inhalation or ingestion of lead-containing compounds. Leaded gasoline (pre-1976), lead paint and dust (in older homes), and

industrial emissions are responsible for a large portion of environmental lead. Chronic exposure to lead has been linked to adverse health outcomes in a number of organ systems including the nervous system, liver, kidneys, reproductive, endocrine, skeletal, gastrointestinal and cardiac systems (Needleman et al., 1990; Philip and Gerson, 1994; Baselt, 2000). Given community concerns, the potential confounding effects of the health effects described, it is proposed that both mercury and lead be included in the Metal Tests in the present study.

3.3.6 Cigarette Smoking

Exposure to cigarette smoke has long been recognized as a leading cause of adverse health effects on respiratory symptoms and diseases (Bartal, 2001). Not only can smoking cause lung disease, it can make the lungs more susceptible to the negative pulmonary effects of other agents. In addition to its pulmonary effects, exposure to cigarette smoke may have other health consequences, including various types of cancer, cardiovascular disease, suppression of the immune system, and reproductive disorders (Bartal, 2001; Tengs and Osgood, 2001; Sopori, 2002). Given the broad effects of tobacco on human health, exposure to cigarette smoke should be considered a potential health confounder.

There are several biomarkers available to assess cigarette smoke exposure. For example, carboxyhaemoglobin (COHb) is often increased in smokers and can be assessed by single breath carbon monoxide (CO) levels (Middleton and Morice, 2000). Additionally, nicotine, the active substance in cigarette smoke, is intensively metabolized in the liver

and oxidized into cotinine (Berny et al., 2002). The measurement of cotinine allows the differentiation between non-exposed and tobacco-exposed individuals. As such, both breath CO and plasma cotinine tests will be included as part of the medical test battery to gauge cigarette smoke exposure, and to validate self-reported smoking patterns.

3.4 Study Limitations

Many factors can influence health and confound the measures of health including: age, gender, family history, as well as social, physical and economic environment. These have been taken into account in the CHAP project wherever possible. There has been the addition of the three confounding metals, lead, mercury and cadmium. We will be able to determine the levels of CoCs in the body but where there is the presence of multiple chemicals, it may be difficult to deduce any association with one particular contaminant. In evaluating the exposure and levels of CoCs in the body, it should be noted that the exposure does not indicate the level of lifetime exposure or the highest exposure that an individual has had. The level of CoCs detected in the body measure the level of metal at that moment of time. The measures will not be able to differentiate between recent exposure or levels of metal from a previous or historical exposure, in addition the measures will not be a reflection of the highest exposure or the duration of the exposure. The tests for CoCs will only measure the presence of CoCs and not the end organ effect of the CoCs.

In measuring any parameter of health, it needs to be noted that measurements need to be evaluated in reference to other measures in the body. An elevation of one parameter may seem to be an issue as it is out of range and yet when viewed holistically, the data can be normal for the age and gender. The data will all be viewed accordingly and any values that are of concern will be put into context both in the analysis and in communication with the subject and local physician. This is especially important when one considers that in general there is a background level of most metals and trace elements in everybody. The levels of CoCs found in the community of Port Colborne will be compared to standard reference ranges. In the analysis, the confounder data collected will be utilized to add context to the data. There may be instances where the very nature of the confounder will result in the fact that an outcome could be due to more than one cause. Confounders include, diet and food in general. Arsenic levels can be elevated by the ingestion of shellfish. This can be differentiated by utilizing a fractionated arsenic measure methodology that will identify organic and non-organic arsenic. The asthma symptoms and signs could be due to atopy (genetic susceptibility to allergies) in the subject, and therefore the person has hyperreactive airways to a number of airborne irritants. Hypersensitivity to nickel could be confounded by the level of jewelry that pierces the skin. Cobalt could be elevated due to the presence of a prosthesis device. This will all be clearly addressed during the review of each participants data and in the analysis. Other confounders that will be taken into account are lifestyle factors, such as smoking or use of alcohol. These are associated with many health risks including cancer and heart disease, use of prescription medications, OTC, Health supplements, such as those that contain vitamin B12 and other natural products. The use of medicinal products,

although treating one set of specific symptoms, may effect other haematological parameters. For example the use of Lithium can increase TSH levels, certain anti-inflammatory drugs can effect T-4 levels, codeine can effect liver enzyme levels.

Additional study limitations that bear mentioning include: the sample size of Port Colborne residents will preclude assessment of certain outcomes that occur at low frequencies (i.e., cancer); the fact that the cross-sectional design of the present study provides only a snapshot that makes it difficult to discern a temporal pattern (cause-effect relationship); and limitation of exposure data.

